14.2 Secondary Analysis

If primary endpoint is not met, secondary endpoint findings will be considered exploratory. The secondary efficacy analyses will include a comparison between the two treatment arms for outcomes given in section 10.2.

Glycaemic metrics will be based on CGM glucose levels collected during the 12 week intervention period. Similar linear models as the primary outcome will be used to compare the between treatment difference. For those metrics which have highly skewed distribution, a ranked normal

score transformation of outcome data will be applied in the regression model. P-value <0.05 will be used to define statistical significance for selected secondary outcomes (HbA1c, glucose CV, %time below 3.9 mmol/l, %time above 10.0 mmol/l, total daily insulin and change in body weight). For other outcomes, in order to reduce the inflation of type I error caused by multiple comparisons, p-value <0.01 will be used to define statistical significance.

A subset of CGM and insulin metrics will also be tabulated separately for daytime period (8AM-12PM) and nighttime period (12PM-8AM).

- Percent time with glucose in target range of 3.9 to 10.0 mmol/l (70-180 mg/dl)
- Mean glucose
- Glucose variability as measured by standard deviation
- Percent time with glucose level <3.5 mmol/l (63 mg/dl)
- Amount of delivered insulin

Trends in CGM data collected within intervention arms will be evaluated on a 4-weekly basis.

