Study objectives	
1. EFFICACY: The objective is to assess efficacy of day and night automated closed loop glucose control combined with pump suspend feature in maintaining CGM glucose levels within the target range from 3.9 to 10 mmol/l (70 to 180mg/dl), as compared to sensor augmented insulin pump therapy.
 
2. SAFETY: The objective is to evaluate the safety of day and night automated closed loop glucose control combined with pump suspend feature, in terms of episodes of severe hypoglycaemia and other adverse events.
 
3. UTILITY: The objective is to determine the frequency and duration of the use of the automated closed loop system.
 
4. PSYCHOSOCIAL: Subjects' and family members' perception in terms of life-style change, diabetes management and fear of hypoglycaemia will be assessed using validated questionnaires and semi-structured qualitative interviews.

Study design	An open-label, multi-centre, multi-national,

	randomised, single-period, parallel group study, contrasting day and night automated closed loop glucose control combined with pump suspend feature with sensor augmented insulin pump therapy.
Primary endpoint	
 Time spent in the target glucose range (3.9 to 10mmol/l) (70 to 180mg/dl)
Secondary endpoint(s)	
 Time spent below target glucose (3.9mmol/l)(70mg/dl) Time spent above target glucose (10.0 mmol/l) (180 mg/dl) HbA1c levels at 12 weeks Average, standard deviation, and coefficient of variation of glucose levels Time with glucose levels < 3.5 mmol/l (63 mg/dl) and <2.8 mmol/l (50 mg/dl) Time with glucose levels in significant hyperglycaemia (glucose levels > 16.7 mmol/l) (300mg/dl) Total, basal and bolus insulin dose AUC of glucose below 3.5mmol/l (63mg/dl) Number of pump suspend events (applicable to intervention arm) Change in body weight from screening to end of study 
Secondary endpoint will be based on sensor glucose data.

Exploratory endpoint(s)	Day (08:00 to 24:00) vs. night (00:00 to 08:00) glucose control, monthly trends in glucose control and insulin delivery, relationships between compliance and glucose outcomes, differences between youth and adults in outcomes.

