14.1 Primary Analysis

The primary analysis will evaluate between group difference in the time (midnight to midnight) spent in the target glucose range from 3.9 to 10 mmol/l (70 to 180mg/dl) based on CGM glucose levels during the 12 week free living phase.

A 5% significance level will be used to declare statistical significance for the primary outcome comparison.

The primary analysis will follow the intention-to-treat principle. It will include all randomized subjects, the data from whom will be analysed in the group to which the subjects were assigned through randomisation regardless of the actual treatment received. Data will not be truncated due to protocol deviations.

Mean (SD) for % time spent in the target range will be tabulated by treatment group. A linear model will be used to compare the difference between the two intervention arms, while adjusting for baseline % time spent in the target glucose range and random site effect. A 95% confidence interval will be reported for the difference between the treatment groups based on the linear model. Normality of the residuals will be assessed. If the residuals have highly skewed distribution, then ranked normal score transformation of outcome data will be applied in the regression model. However, previous experience suggests that % time in target glucose range will follow an approximately normal distribution. A detailed analysis plan will be provided separately.

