14.10 Sample Size and Power Calculations

Based on our previous day-and-night closed loop studies and a conservative estimate of 10 percentage points improvement in time when glucose is in target glucose range with a SD of 14.5 percentage points, 76 subjects are required to achieve 85% power and an alpha level of 0.05 (two-tailed). 84 are planned to be randomised to allow for dropouts. It is expected that 95 or more subjects will be recruited; recruitment will continue until it is anticipated that a sufficient number have been enrolled to meet the randomisation goal. Randomisation target may be exceeded since all of the subjects who have initiated the run-in phase will be permitted to continue into the intervention.

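### Section 14.2 writes the day and night windows with 12PM where midnight is almost certainly meant, which contradicts the synopsis; a minor correction to an exploratory tabulation

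*Protocol*

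**What the plan says.** Two places in the protocol define this trial's own day and night windows.

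- Section 2 (Study Synopsis, exploratory endpoints) uses 24-hour notation: "Day (08:00 to 24:00) vs. night (00:00 to 08:00) glucose control".
- Section 14.2 (Secondary Analysis) uses 12-hour notation. A subset of metrics will be "tabulated separately for daytime period (8AM-12PM) and nighttime period (12PM-8AM"). The five metrics listed there are percent time in 3.9 to 10.0 mmol/l, mean glucose, glucose SD, percent time below 3.5 mmol/l, and the amount of insulin delivered.

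The primary analysis in section 14.1 has its own window. It concerns the "between group difference in the time (midnight to midnight) spent in the target glucose range", so it covers the whole 24 hours.

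Other night windows appear in section 4.8 and Appendices 1 and 2 (midnight to 07:00, and 23:00 to 07:00). They describe earlier studies and do not define anything for this trial.

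**The concern.** In standard usage 12PM is noon. Section 14.2 therefore calls 08:00 to noon daytime and noon to 08:00 nighttime, which cannot be squared with the synopsis. The sentence is an operative analysis rule, not background text, and it governs five tabulated metrics.

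If the windows were coded as written, the night column would mix afternoon, evening and true night, and the day column would keep only the morning. The amount of insulin delivered is the most exposed metric. If it is tabulated as a total, it depends directly on the length of the window, and boluses for afternoon and evening meals would count as night insulin. If an analyst instead corrects the windows silently, the tables depart from the written rule, and section 14.11 asks that departures from the statistical plan be recorded and agreed.

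**Working it through.** **Inputs.** Windows from section 14.2: 8AM to 12PM, and 12PM to 8AM. Windows from the synopsis: 08:00 to 24:00, and 00:00 to 08:00.

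**Window lengths.** Length = (end − start) modulo 24.

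| Source | Day | Night |
|---|---|---|
| Synopsis | 24 − 8 = 16 h | 8 − 0 = 8 h |
| 14.2, 12PM as noon | 12 − 8 = 4 h | (8 − 12) mod 24 = 20 h |
| 14.2, 12PM as midnight | 24 − 8 = 16 h | 8 − 0 = 8 h |

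Read literally, section 14.2 does not reproduce the synopsis. Read with 12PM as midnight, it reproduces it exactly.

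**Hours that change category.** The hours from 12:00 to 24:00 are day in the synopsis and night in the literal 14.2. That is 12 of 24 hours, half of every day. It is 12/16 = 75% of the synopsis day and 12/20 = 60% of the literal night.

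**Effect on an amount.** For insulin as a total at a constant hourly rate (an assumption), the literal night figure would be 20/8 = 2.5 times the intended one, and the literal day figure 4/16 = 0.25 times.

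**Illustration for time in range.** The protocol gives no separate day and night effects for this trial, so the pairs below are assumptions. The calculation also assumes even CGM coverage across the hours and a uniform effect within the true day and the true night.

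Literal night effect = (8 × night effect + 12 × day effect) / 20.

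| Assumed night / day effect (points) | Literal night effect | Shortfall against true night effect |
|---|---|---|
| 15 / 7 | (120 + 84)/20 = 10.2 | (15 − 10.2)/15 = 32% |
| 18 / 5 | (144 + 60)/20 = 10.2 | (18 − 10.2)/18 = 43% |
| 12 / 8 | (96 + 96)/20 = 9.6 | (12 − 9.6)/12 = 20% |

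**What is not touched.** The primary endpoint runs midnight to midnight (section 14.1). The glucose endpoints in section 10.2 carry no day or night split. The safety analyses in section 14.3 use event counts. The sample size in section 14.10 uses a 10-point difference with "SD of 14.5 percentage points, 76 subjects are required to achieve 85% power and an alpha level of 0.05 (two-tailed"); none of these inputs depends on a day or night window, and the stated 76 reproduces (38 per arm, power 0.852).

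**The case against.** The strongest reply is that this is a clerical slip with one sensible reading. A nighttime that starts at noon is absurd on its face, and the synopsis gives the intended windows in unambiguous notation, so a careful analyst would resolve it. Section 14.1 also announces a separate detailed analysis plan. Programming would normally follow that plan, which is not among the documents at hand, and nothing shows that the slip carries into it. Finally, the synopsis classes day versus night control as exploratory, no participant is affected, and the tables can be re-cut from stored data.

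All of this stands, and it settles the weight of the point as minor. It does not remove the contradiction: the protocol itself fixes the windows in its analysis section, and fixes them in a form that is right only if the reader assumes an error.

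Two stronger readings are tempting, and the documents do not support them.

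- A reader might infer that every day and night result will be wrong. That follows only if someone codes noon literally and nobody notices.
- A reader might infer that the error destroys comparability with the earlier overnight studies. Those studies used 23:00 to 07:00 (Appendix 1) and midnight to 07:00 (section 4.8, Appendix 2), with a target of 3.9 to 8.0 mmol/l. This trial uses 3.9 to 10.0 mmol/l, and its 00:00 to 08:00 window matches neither, so strict comparability is absent even after the correction. The earlier day-and-night study (section 4.9, Appendix 3) shares this trial's target, but the protocol does not state the clock times behind its day and night results.

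**Conclusion.** The inconsistency is real. Section 14.2 read literally gives 4 and 20 hours, the synopsis gives 16 and 8 hours, and the 12 hours from noon to midnight are classified differently. It is most likely 12PM written for midnight; that inference rests on the exact agreement of the midnight reading with the synopsis.

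The reach is limited to the day and night tabulations of five metrics. Under literal coding, 60% of the night window would be afternoon and evening. The 20% to 43% shortfall in the night effect rests wholly on assumed effects and even CGM coverage, and should be quoted only as an illustration. This is a minor wording correction. It gives no reason to doubt the primary comparison or the whole-day secondary results.

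**What to change.** In section 14.2, replace the two windows with 24-hour clock times that match the synopsis: daytime 08:00 to 24:00, nighttime 00:00 to 08:00. Confirm that the separate analysis plan uses the same times, and do both before the day and night tables are programmed.

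The cost is one line of wording. It needs no new data, no participants and no change in conduct, and it introduces no new definition. If any tables have already been produced with noon as the boundary, they can be re-run from the stored CGM and pump data.

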14.3 Safety Analysis

Below safety outcomes will be tabulated by treatment group:

- Number of subjects with any diabetic ketoacidosis events
- Number of episodes of diabetic ketoacidosis events per subject and incidence rate per 100-person years
- Number of subjects with any severe hypoglycaemia events
- Number of episodes of severe hypoglycaemia events per subject and incidence rate per 100-person years
- Number of subjects with any severe hyperglycaemia events as defined by fingerprick glucose >16.7 mmol/l (>300 mg/dl) and plasma ketones >0.6 mmol/l
- Number of episodes of severe hyperglycaemia events per subject and incidence rate per 100-person years

Above safety data will be tabulated for all subjects in the two intervention periods, including drop-outs and withdrawals, irrespective of whether CGM data are available and irrespective of whether closed loop was operational. All adverse events will be listed for the entire study duration.

If there are enough observed events to allow formal statistical modelling for above safety outcomes, the following analyses will be conducted. The event rates will be compared using a Poisson regression model adjusting for random site effect. If outliers exist, a robust Poisson regression model will be used instead. Binary variables will be compared using a logistic regression model

adjusting for random site effect. Models involve severe hypoglycaemia events will also adjust for severe hypoglycaemia in the previous 6 months before enrolment.

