9.15 Participant Withdrawal Criteria

The following pre-randomisation withdrawal criteria will apply:

1. Subject is unable to demonstrate safe use of study insulin pump and / or CGM during run-in period as judged by the investigator
2. Subject fails to demonstrate compliance as mentioned in section 9.5.1 with study insulin pump and / or CGM during run-in period

The following pre- and post-randomisation withdrawal criteria will apply:

3. Subjects may terminate participation in the study at any time without necessarily giving a reason and without any personal disadvantage
4. Significant protocol violation or non-compliance
5. Any severe hypoglycaemia event related to use of the closed loop system
6. Two severe hypoglycaemia events unrelated to the use of the closed loop system
7. DKA unrelated to infusion site failure and related to the use of the closed loop system
8. Decision by the investigator or the sponsor that termination is in the subject's best medical interest
9. Subject becomes pregnant during the study period
10. Allergic reaction to insulin
11. Allergic reaction to adhesive surface of infusion set or glucose sensor
12. If patient continues to use pump suspend feature in the control group despite advice to the contrary

Subjects who are withdrawn for reasons stated in (4) to (12) will be invited to provide blood sample at the end of the planned study intervention for the assessment of HbA1c.

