14.9 Statistical Methods

The respective values obtained during the 12-week randomised interventions contrasting the closed loop combined with pump suspend feature against the sensor augmented pump therapy will be compared using independent samples statistical techniques. For non-normally distributed parameters transformation or nonparametric analyses will be used.

Primary analysis will be a single comparison and no attempt will be formally made to control the overall type I error rate for the secondary outcomes. A 5% significance level will be used to declare statistical significance for the primary comparison.

Severe hypoglycaemic events and ketone-positive hyperglycaemia will be tabulated in each treatment group, which will be compared using repeated measures logistic regression (generalised estimator equation).

Safety data including severe hypoglycaemia events and ketone-positive hyperglycaemia will be tabulated for all subjects, including drop-outs and withdrawals, irrespective of whether CGM data are available and irrespective of whether closed loop was operational.

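### The default Poisson model for repeat-event rates ignores differences between participants, and its robust fallback is triggered by outliers rather than overdispersion

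*Protocol*

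**What the plan says.** Section 14.3 (Safety Analysis) lists diabetic ketoacidosis, severe hypoglycaemia and severe hyperglycaemia with ketones. Each is tabulated as participants with any event and also as episodes per participant, for example "Number of episodes of severe hyperglycaemia events per subject and incidence rate per 100-person years".

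Modelling is conditional: "If there are enough observed events to allow formal statistical modelling for above safety outcomes, the following analyses will be conducted". The default for rates is: "The event rates will be compared using a Poisson regression model adjusting for random site effect". The alternative is: "If outliers exist, a robust Poisson regression model will be used instead". Binary outcomes get logistic regression with a random site effect. Models for severe hypoglycaemia also adjust for severe hypoglycaemia in the 6 months before enrolment.

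Section 14.9 (Statistical Methods) says that severe hypoglycaemic events and ketone-positive hyperglycaemia will be tabulated by group, "which will be compared using repeated measures logistic regression (generalised estimator equation").

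Section 9.15 (Participant Withdrawal Criteria) includes "Any severe hypoglycaemia event related to use of the closed loop system" and "Two severe hypoglycaemia events unrelated to the use of the closed loop system". It also lists ketoacidosis that is related to the closed loop and not to infusion site failure. It has no criterion based on repeat hyperglycaemia with ketones.

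**The concern.** A Poisson likelihood sets the variance of a participant's count equal to its mean. Participants with type 1 diabetes differ in their tendency to have events, so variance will usually exceed the mean even when no single participant stands out. The random site effect covers variation between centres only. The one participant-level covariate, prior severe hypoglycaemia, applies only to the severe hypoglycaemia models. It is also the same for every eligible participant, because exclusion criterion 8 in section 7.3 bars anyone with an episode in that window.

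The fallback is tied to outliers, which is a different feature of the data. The choice between models is made after the counts are seen, in an open-label trial. If robust means downweighting extreme participants rather than a sandwich variance, the standard error is not directly corrected, and those with the most safety events would count least.

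At stake is the width of the confidence intervals for the safety rate ratios. If they are too narrow, a chance difference in either direction could be read as a safety signal or a safety advantage.

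**Working it through.** **Inputs from the protocol.** 84 randomised and a 12-week intervention (section 14.10 and the synopsis). The allocation ratio is not stated; 42 per arm is assumed.

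**Inputs assumed.** The protocol gives no expected rate or dispersion for these analyses. Let μ be the mean number of events per participant over 12 weeks and k the variance of a gamma frailty with mean 1, so Var(Y) = μ(1 + kμ). Range shown: μ 0.1 to 1.0, k 0.5 to 4. Site effect left out, equal follow-up, no true difference.

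**The plan's own figure.** The only sample size statement is for the primary endpoint: "76 subjects are required to achieve 85% power and an alpha level of 0.05 (two-tailed"). With a difference of 10 and SD 14.5, n per arm = 2 × (1.960 + 1.036)² × (14.5/10)² = 37.8, rounded up to 38, so 76 in all. It reproduces, but it says nothing about the safety events.

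**Standard error.** The Poisson standard error of the log rate ratio is √(1/S₁ + 1/S₂), where S₁ and S₂ are the event totals. The true standard deviation is larger by about √(1 + kμ):
- μ = 0.25, k = 4: √2.0 = 1.41 (simulated 1.40)
- μ = 0.5, k = 4: √3.0 = 1.73 (simulated 1.72)

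**Type I error.** 40,000 simulated null trials per setting, two-sided nominal 5%. Four procedures: Poisson throughout; the stated switch with an outlier read as any participant with at least 3 events; the same with at least 5; sandwich variance throughout. In the switched procedures, robust is read as sandwich variance.

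| μ | k | Poisson | Switch at ≥3 | Switch at ≥5 | Sandwich |
|---|---|---|---|---|---|
| 0.1 | 1 | 1.7% | 1.6% | 1.7% | 1.4% |
| 0.1 | 4 | 3.3% | 2.3% | 3.1% | 1.8% |
| 0.25 | 0.5 | 5.6% | 4.8% | 5.5% | 4.6% |
| 0.25 | 1 | 6.7% | 5.1% | 6.4% | 4.9% |
| 0.25 | 4 | 14.2% | 6.7% | 10.2% | 6.4% |
| 0.5 | 1 | 10.1% | 5.6% | 7.9% | 5.6% |
| 0.5 | 4 | 25.0% | 7.6% | 9.0% | 7.5% |
| 1.0 | 1 | 16.4% | 5.9% | 6.3% | 5.9% |
| 1.0 | 4 | 37.0% | 7.7% | 7.7% | 7.7% |

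The mismatch of trigger and problem shows at μ = 0.5, k = 1. Only 29% of trials contain a participant with 5 or more events, so under that reading 71% would stay with plain Poisson although the variance is 1.5 times the mean.

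**Severe hypoglycaemia.** If follow-up ends at a second event, as section 9.15 suggests, Poisson error for k from 1 to 4 is 1.7% to 2.1% (μ = 0.1), 5.5% to 7.5% (μ = 0.25) and 6.9% to 9.9% (μ = 0.5). The inflation is much smaller than without the limit. The background in section 4 gives one episode per year in the average patient, 1 × 12/52 = 0.23 per 12 weeks. Section 7.3 excludes people with a recent episode, so a lower rate is plausible here.

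**Sections 14.3 and 14.9 side by side.** For severe hypoglycaemia and ketone-positive hyperglycaemia, 14.3 gives Poisson regression for rates and site-adjusted logistic regression for binary outcomes. Section 14.9 gives generalised estimating equations with a logistic model for the same events. The effect measures differ (rate ratio against odds ratio), as does the treatment of correlation within a participant. Neither section refers to the other.

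**The case against.** The strongest reply is that the plan does not use plain Poisson throughout. It has a switch, and with an outlier read as 3 or more events and robust as sandwich variance, the switch does almost as well as sandwich variance throughout (7.6% against 7.5% at μ = 0.5, k = 4). This stands, and it limits the size of the point. What remains is that performance depends on the reading: at 5 or more events, the error reaches 10.2% at μ = 0.25, k = 4.

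A reader might infer that a few participants with many episodes would break the analysis. The documents do not support that: this is the pattern that an outlier rule is most likely to catch. The gap is diffuse, moderate overdispersion.

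It can also be said that 14.9 already allows for correlation within participants. It does, but by a method that conflicts with 14.3 and does not cover ketoacidosis.

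Finally, definitions of outlier and robust may be in the separate analysis plan announced in section 14.1. Their absence here is therefore not the point. The point is the default model and the kind of trigger, which the protocol itself states.

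**Conclusion.** The point holds in limited form. Section 14.3 makes a model that ignores differences between participants the default, and guards it with a condition aimed at a different problem. With 42 per arm, μ 0.25 to 1.0 and k 0.5 to 4 (all assumed), unswitched Poisson rejects about 6% to 37%, the stated switch about 5% to 10%, and sandwich variance throughout about 5% to 8%. The first range is not the error rate of the plan, although it could be mistaken for it, because it leaves out the switch.

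The exposure is mainly severe hyperglycaemia with ketones. Repeat severe hypoglycaemia is restricted by section 9.15, and with about 0.1 events per participant there is no excess for any outcome.

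A reader might also infer that the trial would formally declare a false safety benefit or harm. The documents do not go that far: the outcomes are tabulated first, modelling is conditional on enough events, and section 14.3 attaches no significance threshold to these tests. The primary result is untouched. The conflict between 14.3 and 14.9 needs no assumption and stands by itself. Overall severity is low.

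**What to change.** In section 14.3, specify the rate model from the start either as Poisson regression with robust (sandwich) variance or as negative binomial regression, with log person-time as offset. Delete the condition about outliers. In section 14.9, remove or align the generalised estimating equations sentence, so that one method is named for each event type and for each form of outcome (rate or binary).

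The cost is a few sentences of wording and no new data. Intervals become slightly wider. Sandwich variance stays mildly liberal at this sample size when dispersion is high (7.7% at μ = 1.0, k = 4).
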